3.3 Inclusion of Women and Minorities

The study is open to any individual who meets above eligibility criteria without discrimination based on race or gender. We do not anticipate that inclusion or exclusion criteria will negatively affect recruitment or retention of underrepresented minorities.

4. REGISTRATION PROCEDURES

4.1 General Guidelines for DF/HCC Institutions

Institutions will register eligible participants in the Clinical Trials Management System (CTMS) OnCore. Registrations must occur prior to the initiation of any protocol-specific therapy or intervention. Any participant not registered to the protocol before protocol-specific therapy or intervention begins will be considered ineligible and registration will be denied.

An investigator will confirm eligibility criteria and a member of the study team will complete the protocol-specific eligibility checklist.

Following registration, participants may begin protocol-specific therapy and/or intervention. Issues that would cause treatment delays should be discussed with the Overall Principal

Version Date: 12/21/22

Investigator (PI). If the subject does not receive protocol therapy following registration, the subject must be taken off study in the CTMS (OnCore) with an appropriate date and reason entered

1.1 Registration Process for DF/HCC Institutions

Applicable DF/HCC policy (REGIST-101) must be followed.

1. TREATMENT PLAN

1.1 Treatment Regimen

Treatment will be administered on an outpatient basis every 4 weeks, with 28 consecutive days defined as a treatment cycle. Expected toxicities and potential risks as well as dose modifications for zafirlukast are described in Section 6 (Expected Toxicities and Dosing Delays/Dose Modification).

	Reg	gimen Descri	ption		
Agent	Premedications; Precautions	Dose	Route	Schedule	Cycle Length
Zafirlukast	None	40 mg	Oral tablets	Twice daily	28 days

The first cohort of 4 participants will receive zafirlukast 40 mg (two 20 mg tablets) twice daily. In the absence of drug related serious adverse events (grade 3 or 4 possibly or probably related), an additional cohort of 4 patients will be enrolled at 80 mg twice daily.

Participants will be requested to maintain a medication diary of each dose of medication. The medication diary will be returned to clinic staff at the end of each cycle.

1.2 Pre-Treatment Criteria

5.1.1. Cycle 1, Day 1

- Laboratory assessments recorded within 14 days of signing consent may be used to determine eligibility and does not have to be repeated (except complete blood count)
- Absolute neutrophil count > 1,000/mcL
- Platelet count > 90,000/mcL
- Participants must be able to tolerate PO tablets

5.1.2. Subsequent Cycles

• Toxicities possibly related to zafirlukast must return to grade 2 or less

1.3 Agent Administration

Zafirlukast will be supplied as oral tablets.

Cohort 1: Two tablets (total of 40 mg) will be consumed twice daily. Cohort 2: Four tablets (total of 80 mg) will be consumed twice daily.

Dose modifications will not be made. Tablets will be dispensed from the research pharmacy on day 1 of each cycle. The tablets will be packaged as a 30-day supply (to allow for unexpected occurrences such as dropped tablet).

Tablets should be taken without food. Food decreases the bioavailability of zafirlukast by 40%. Therefore, participants will be instructed to take zafirlukast on an empty stomach, 1 hour before and 2 hours after meals. Missed doses must be taken within four hours of scheduled dose. If longer than four hours, or if dose vomited, skip dose. Subjects will keep a drug diary that will be provided to them by the study team. Subjects will be instructed to return any unused drug. The unused returns will be counted by pharmacy and destroyed on-site per policy.

1.4 General Concomitant Medication and Supportive Care Guidelines

Because there is a potential for interaction of zafirlukast with other concomitantly administered drugs through the cytochrome P450 system, the case report form must capture the concurrent use of all other drugs, over-the-counter medications, or alternative therapies. The Overall PI should be alerted if the participant is taking any agent known to affect or with the potential to affect selected CYP450 isoenzymes. Appendix B presents guidelines for identifying medications/substances that could potentially interact with the study agent(s).

1.5 Criteria for Taking a Participant Off Protocol Therapy

Duration of therapy will be ongoing (+/- 7 days inclusion of windows) for up to 12 cycles or until one of the following criteria apply:

- Intercurrent illness that prevents further administration of treatment
- Unacceptable adverse event(s)
- Participant demonstrates an inability or unwillingness to comply with the oral medication regimen and/or documentation requirements
- Participant decides to withdraw from the study, or general or specific changes in the
 participant's condition render the participant unacceptable for further treatment in the
 opinion of the treating investigator
- Clinical or radiographic progression of ovarian cancer
- Doubling the pre-treatment CA-125 value (confirmed at least 1 week apart)
- Grade 3 or 4 hemorrhage and/or symptomatic bleeding in a critical area or organ such as intracranial, intraspinal, intraocular, retroperitoneal, intra-articular or pericardial, or intramuscular with compartment syndrome, and/or bleeding causing a fall in hemoglobin level > 2 g/dL or bleeding leading to a transfusion of > 2 units of packed red blood cells

Version Date: 12/21/22

Participants will be removed from the protocol therapy when any of the criteria listed above applies. The reason for removal from protocol therapy, and the date the participant was removed, must be documented in the study-specific case report form (CRF). Alternative care options will be discussed with the participant.

In the event of unusual or life-threatening complications, participating investigators must immediately notify the Principal Investigator, [name] at [contact].

1.6 Duration of Follow Up

Following completion of treatment participants will be followed for a final 30 days post last dose visit. All AEs and SAEs will be collected during this time. After the completion of the 30 day post last dose follow up, participants may come off study. Participants removed from study treatment for unacceptable adverse events will be followed until resolution or stabilization of the adverse event. Participants who have related unresolved AEs should be followed until resolution of the adverse event or up to 30 days post last dose, whichever occurs later. Participants removed from active treatment for reasons listed in section 1.5, will be followed for 30 days post last dose, prior to coming off study.

1.7 Criteria for Taking a Participant Off Study

Participants will be removed from study when any of the following criteria apply:

- Completed protocol defined procedures and follow-up
- Lost to follow-up
- Withdrawal of consent for data submission

Death

The reason for taking a participant off study, and the date the participant was removed, must be documented in the case report form (CRF). In addition, the study team will ensure the participant's status is updated in OnCore in accordance with REGIST-OP-1

2. DOSING DELAYS/DOSE MODIFICATIONS

Dose delays will be made as indicated in the following table(s). The descriptions and grading scales found in the revised NCI Common Terminology Criteria for Adverse Events (CTCAE) version 5.0 will be utilized for dose delays and dose modifications. A copy of the CTCAE version 5.0can be downloaded from the CTEP website

 $\underline{http://ctep.cancer.gov/protocolDevelopment/electronic_applications/ctc.htm}.$

Thrombocytopenia	Management/Next Dose for Zafirlukast
≤ Grade 1	No change in dose
Grade 2	No change in dose
Grade 3	Hold until \leq Grade 1. Resume at same dose level.
Grade 4	Do not restart

Version Date: 12/21/22

ALT/AST	Management/Next Dose for Zafirlukast
≤ Grade 1	No change in dose
Grade 2	Hold until within normal range. Resume at same dose level.
Grade 3	Do not restart
Grade 4	Do not restart

Bilirubin	Management/Next Dose for Zafirlukast
≤ Grade 1	No change in dose
Grade 2	Hold until within normal range. Resume at same dose level.
Grade 3	Do not restart.
Grade 4	Do not restart

3. ADVERSE EVENTS: LIST AND REPORTING REQUIREMENTS

Adverse event (AE) monitoring and reporting is a routine part of every clinical trial. The following list of reported and/or potential AEs (Section 7.1) and the characteristics of an observed AE (Section 7.2) will determine whether the event requires expedited reporting **in addition** to routine reporting.

3.1 Expected Toxicities

3.1.1 Adverse Event List(s) for Zafirlukast

Headache 12.9%

Infection 3.5%

Nausea 3.1%

Diarrhea 2.8%

Pain (generalized) 1.9%

Asthenia 1.8% 1.6%

Abdominal Pain 1.8%

Dizziness 1.6%

Myalgia 1.6%

Fever 1.6%

Back Pain 1.5%

Vomiting 1.5%

Liver function testing elevation 1.5%

Dyspepsia 1.3%

Rarely, elevations of one or more liver enzymes have occurred in patients receiving zafirlukast in controlled clinical trials. In clinical trials, most of these have been observed

at doses four times higher than the recommended dose. The following hepatic events (which have occurred predominantly in females) have been reported from post-marketing adverse event surveillance of cases of symptomatic hepatitis (with or without hyperbilirubinemia) without other attributable cause; and rarely, hyperbilirubinemia without other elevated liver function tests. In most, but not all post-marketing reports, the patient's symptoms abated and the liver enzymes returned to normal or near normal after stopping zafirlukast. In rare cases, patients have presented with fulminant hepatitis or progressed to hepatic failure, liver transplantation and death

3.2 Adverse Event Characteristics

• CTCAE term (AE description) and grade: The descriptions and grading scales found in the revised NCI Common Terminology Criteria for Adverse Events (CTCAE) version 5.0 will be utilized for AE reporting. All appropriate treatment areas should have access to a copy of the CTCAE version 5.0. A copy of the CTCAE version 5.0 can be downloaded from the CTEP web site http://ctep.cancer.gov/protocolDevelopment/electronic applications/ctc.htm.

• For expedited reporting purposes only:

- AEs for the agent(s) that are listed above should be reported only if the adverse event varies in nature, intensity or frequency from the expected toxicity information which is provided.
- Other AEs for the protocol that do not require expedited reporting are outlined in the next section (Expedited Adverse Event Reporting) under the sub-heading of Protocol-Specific Expedited Adverse Event Reporting Exclusions.

• **Attribution** of the AE:

- Definite The AE *is clearly related* to the study treatment.
- Probable The AE *is likely related* to the study treatment.
- Possible The AE *may be related* to the study treatment.
- Unlikely The AE *is doubtfully related* to the study treatment.
- Unrelated The AE *is clearly NOT related* to the study treatment.

3.3 Adverse Event Reporting

- 3.3.1 In the event of an unanticipated problem or life-threatening complications treating investigators must immediately notify the Overall PI.
- 3.3.2 Investigators **must** report to the Overall PI any adverse event (AE) that occurs after the initial dose of study treatment, during treatment, or within 30 days of the last dose of treatment on the local institutional SAE form.

3.3.3 DF/HCC Adverse Event Reporting Guidelines

Investigative sites within DF/HCC will report AEs directly to the DFCI Office for Human Research Studies (OHRS) per the DFCI IRB reporting policy.

3.4 Reporting to Hospital Risk Management

Participating investigators will report to their local Risk Management office any participant safety reports, sentinel events or unanticipated problems that require reporting per institutional policy.

3.5 Routine Adverse Event Reporting

All Adverse Events must be reported in routine study data submissions to the Overall PI on the toxicity case report forms. AEs reported through expedited processes (e.g., reported to the IRB, FDA, etc.) must also be reported in routine study data submissions.

4. PHARMACEUTICAL INFORMATION

A list of the adverse events and potential risks associated with the investigational administered in this study can be found in Section 7.1.

4.1 Zafirlukast

4.1.1 Description

Zafirlukast is a synthetic, selective peptide leukotriene receptor antagonist (LTRA), with the chemical name 4-(5-cyclopentyloxycarbonylamino-1-methyl-indol-3-ylmethyl)-3-methoxy-N-o-tolylsulfonylbenzamide.

Zafirlukast is rapidly absorbed following oral administration. Peak plasma concentrations are generally achieved 3 hours after oral administration. The absolute bioavailability of zafirlukast is unknown. In two separate studies, one using a high fat and the other a high protein meal, administration of zafirlukast with food reduced the mean bioavailability by approximately 40%.

Zafirlukast is more than 99% bound to plasma proteins, predominantly albumin. The degree of binding was independent of concentration in the clinically relevant range. The apparent steady-state volume of distribution is approximately 70 L, suggesting moderate distribution into tissues. Studies in rats using radiolabeled zafirlukast indicate minimal distribution across the blood-brain barrier.

Zafirlukast is extensively metabolized. The most common metabolic products are hydroxylated metabolites which are excreted in the feces. The metabolites of zafirlukast identified in plasma are at least 90 times less potent as LTD4 receptor antagonists than zafirlukast in a standard in vitro test of activity. In vitro studies using human liver microsomes showed that the hydroxylated metabolites of zafirlukast excreted in the feces are formed through the cytochrome P450 2C9 (CYP2C9) pathway. Additional in vitro studies utilizing human liver microsomes show that zafirlukast inhibits the cytochrome P450 CYP3A4 and CYP2C9 isoenzymes at concentrations close to the clinically achieved total plasma concentrations.

Version Date: 12/21/22

The apparent oral clearance (CL/f) of zafirlukast is approximately 20 L/h. Studies in the rat and dog suggest that biliary excretion is the primary route of excretion. Following oral administration of radiolabeled zafirlukast to volunteers, urinary excretion accounts for approximately 10% of the dose and the remainder is excreted in feces. Zafirlukast is not detected in urine.

In the pivotal bioequivalence study, the mean terminal half-life of zafirlukast is approximately 10 hours in both normal adult subjects and patients with asthma. In other studies, the mean plasma half-life of zafirlukast ranged from approximately 8 to 16 hours in both normal subjects and patients with asthma. The pharmacokinetics of zafirlukast are approximately linear over the range from 5 mg to 80 mg. Steady-state plasma concentrations of zafirlukast are proportional to the dose and predictable from single-dose pharmacokinetic data. Accumulation of zafirlukast in the plasma following twice-daily dosing is approximately 45%.

4.1.2 Form

Zafirlukast occurs as a fine white to pale yellow amorphous powder. It is supplied in 20 mg tablets for oral administration. Film-coated tablet consist of croscarmellose sodium, lactose, magnesium stearate, microcrystalline cellulose, povidone, hypromellose, and titanium dioxide.

4.1.3 Storage and Stability

Store at controlled room temperature, 20-25°C (68-77°F) [see USP]. Protect from light and moisture. Dispense in the original air-tight container.

4.1.4 Compatibility

No specific compatibility issues.

4.1.5 Handling

No specific measures necessary.

4.1.6 Availability

Zafirlukast will be provided by the research pharmacy. A 30-day supply will be distributed on C1D1 and Day 1 of each cycle moving forward by the local research pharmacy.

4.1.7 Preparation

No specific measures necessary.

4.1.8 Administration

Zafirlukast will be administered orally twice daily.

Version Date: 12/21/22

4.1.9 Ordering

Zafirlukast will be purchased by research pharmacy from commercial supplier.

4.1.10 Accountability

The investigator, or a responsible party designated by the investigator, must maintain a careful record of the inventory and disposition of the agent (investigational or free of charge) using the NCI Drug Accountability Record or another comparable drug accountability form. (See the CTEP website at http://ctep.cancer.gov/protocolDevelopment for the "Policy and Guidelines for Accountability and Storage of Investigational Agents" or to obtain a copy of the drug accountability form.) Participants will record compliance with study treatment in a drug diary that will be provided to them. The drug diary will be collected and re-dispensed at each study visit.

4.1.11 Destruction and Return

At the end of the study, unused supplies of Zafirlukast should be destroyed according to institutional policies. Destruction will be documented in the Drug Accountability Record Form.

5. CORRELATIVE STUDIES

5.1 Laboratory Correlative Studies

The contents of the serum separator tube will be used for CA-125 level determination by the clinical laboratory. CA-125 will be performed in a clinical laboratory using a commercially available assay.

A total of 10 mL of blood will be drawn into blue top tubes (3.2% citrate) in either two 5 mL tubes or one 15 mL tube for correlative labs.

Plasma will be separated at 2100 x G for 20 minutes. First centrifugation should be performed within 1 hour of specimen collection. The plasma layer will be centrifuged a second time at 2100 x G x 20 minutes in a single tube. The plasma supernatant will be transferred to a clean tube leaving the 1 mL at the bottom of the tube undisturbed (to be discarded). The transferred plasma sample will be aliquoted (500 mcL) into 1.5mL Eppendorf tubes.

Tubes will be stored at -80 °C.

Correlative Studies:

- D-dimer will be performed in a research laboratory using a commercially available ELISA.
- Plasma PDI-inhibitory activity: The plasma PDI-inhibitory activity will be measured using a modified DiEGSSG assay[53]. The exposure of the

Version Date: 12/21/22

DiEGSSG probe to exogenous PDI and plasma results in increased fluorescence measured spectrophotometrically and can be used to detect the presence of PDI inhibitor activity.

Plasma samples may be sent for coagulation and PDI-based assays (e.g. platelet-dependent thrombin generation assay) to Western New England University for analysis after a DUA is executed. Samples will be de-identified and coded by study number prior to being sent for analysis.

6. STUDY CALENDAR

Baseline evaluations are to be conducted within 14 days prior to start of protocol therapy. All assessments must be performed prior to administration of any study medication. All study assessments and medications should be administered within +/- 7 days of the protocol-specified date, unless otherwise noted.

										30 Day post	
	Baseline		Cyc	Cycle 1 ^f		Cyc	Cycle 2 ^f	Cycles 3-12 ^f	Off Treatment	Last Dose Follow Up/ Off Study ^{cd}	EDC Timepoints
		Day 1	Day 8	Day 15	Day 22	Day 1	Day 15	Day 1			
Zafirlukast ^B		×				×		×			Day 1 of every Cycle
Informed consent	×										N/A
Demographics	×										Baseline
Medical history	×										Baseline
CT Scan	χ̈										Baseline
Concurrent Medications	-X	X								X	N/A
Physical exam	X	X		X				X	X	X	Baseline
Vital signs	×	×		×				×	X	×	Baseline
Height	×										Baseline
Weight	×	×		×		×		×	X	×	Baseline
Performance status	×	×		×		×		×	×	×	Baseline, Day 1 of every Cycle, Off Treatment, Off Study
CBC w/diff,	×	X	X	X	Х	X	×	X	X	X	Baseline, Cycle 1 Day 1, 8, 15 & 22, Cycle 2 Day 1 & 15, Cycle 3+ Day 1, Off Treatment and Off Study
Serum chemistry ^a	×	Xg	×	×	×	×	×	X	X	×	Baseline, Cycle 1 Day 1, 8, 15 & 22, Cycle 2 Day 1 & 15, Cycle 3+ Day 1, Off Treatment and Off Study
CA-125 Measurement	×	×				×		X	X	X	
Adverse Event Evaluation			×							X	During all visits
Radiologic Evaluation	×	Radic	ologic 1	measure	ements sl	ats should be	e perfor	Radiologic measurements should be performed every 3 cycles*	×		Baseline, Every 3 Cycles during treatment, Off Treatment, each follow-up visit, Off Study. If a Radiologic Evaluation is performed during any other Cycle, it must be captured in InForm.
B-HCG	å										N/A
Drug Diary Review		×				×		X	X		
Other correlative studies ^h		×				×			X		N/A

	Baseline	Cycle 1 ^r	Cycle 2 ^r	Cycles 3-12 ^r	Off Treatment	30 Day post Last Dose Follow Up/ Off Study ^{cd}	EDC Timepoints
Survival		Χ				XX	During all visits

Zafirlukast 40 mg twice daily Total bilirubin, BUN, Creatinine, SGOT [AST], SGPT [ALT]. Serum pregnancy test (women of childbearing potential).

30 Days Post Last Dose: Follow up visits or other contact are required in order to identify SAWs during the 30 days (+/- 7 days) following the end of study treatment. Follow-Up evaluation. After the completion of the 30 days post last dose study visit, participants may be removed from the study. Radiologic measurements should be performed every 3 cycles prior to the initiation of the next cycle. Scans may be performed within a +/-7 day window. Cycles are 28 days in length.

Laboratory assessments recorded within 14 days of signing consent may be used to determine eligibility and does not have to be repeated (except complete blood count) for CIDI if within this window

Refer to section 5.1 CT Scan for Baseline within 4 weeks of registration

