We enrolled a total of four women who received zafirlukast 40 mg twice daily and performed serial CA-125 measurements to assess for tumor response. None of the women demonstrated a decrease in CA-125 following the initiation of zafirlukast. However, in all 4 women the rate of rise of CA-125 was reduced following treatment with zafirulast (Figure 4). Accordingly, the mean change in CA-125 was 0.036 U/mL per day prior to treatment compared with 0.015 U/mL per day following zafirlukast (paired t-test p=0.026). This equated to a mean CA-125 doubling time of 29.8 days in the weeks prior to treatment compared with a mean doubling time of 85.69 days following treatment. There were no grade 3 or higher toxicities observed on study. As shown in Figure 4B, there was only modest inhibition of PDI activity in plasma as measured by Di-eosin-

GSSG assay. In the study subject who demonstrated the greatest PDI inhibition there was the CA-125 doubling was most pronounced. These data suggest that higher doses of zafirlukast may provide additional PDI inhibitory activity and further inhibit ovarian cancer cell growth.

[figure not shown]

Figure 4. CA-125 doubling time following zafirlukast in women with ovarian cancer. A) Comparison of CA-125 doubling time before and after start of zafirlukast. B) Inhibition of plasma PDI activity before and 28 days following initiation of zafirlukast.

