9.2 Sample Size, Accrual Rate and Study Duration

Version Date: 12/21/22

In the 4 women treated with zafirlukast 40 mg twice daily, there were no responses in terms of decline of CA-125. However, However, the mean change in CA-125 was 0.036 U/mL per day prior to treatment compared with 0.015 U/mL per day following zafirlukast (paired t-test p=0.026). This equated to a mean CA-125 doubling time of 29.8 days in the weeks prior to treatment compared with a mean doubling time of 85.69 days following treatment.

A second cohort of 4 women at 80 mg twice daily will be enrolled to assess whether CA-125 doubling time is significantly prolonged compared with pre-treatment values and whether we observe PDI inhibitory activity in plasma using Di-eosin-GSSG assay.

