9.5 Analysis of Exploratory Objectives

- Changes PDI and ERp57 inhibitory activity in plasma, platelet-dependent thrombin will be performed by paired t-test analyses comparing baseline with C2D1 samples.
- Determine progression free survival (PFS)
- Assess the incidence of venous thromboembolism
- Assess incidence of major hemorrhage and clinically relevant non-major bleeding

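### A compliant late C2D1 visit can fall after the 30-day tablet supply ends, so the PDI sample may be off drug; separately, sections 1.5 and 7.2 confirm a CA-125 doubling at different intervals

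*Combined protocol and SAP*

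**What the plan says.** **Supply and sampling.** Section 1.1 (Treatment Regimen) sets a 28-day cycle. Section 1.3 (Agent Administration) says "The tablets will be packaged as a 30-day supply (to allow for unexpected occurrences such as dropped tablet", and section 4.1.6 says "A 30-day supply will be distributed on C1D1 and Day 1 of each cycle moving forward by the local research pharmacy". No other resupply is described. Section 6 says "All study assessments and medications should be administered within +/- 7 days of the protocol-specified date, unless otherwise noted", and nothing in the text gives C2D1 or its correlative blood draw a narrower window. The calendar places correlative samples at C1D1, C2D1 and Off Treatment. Section 9.5 analyses PDI and ERp57 inhibitory activity and platelet-dependent thrombin by paired t-test, "comparing baseline with C2D1 samples".

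**Role of the PDI sample.** PDI activity is an exploratory objective, but section 9.2 names as one of two purposes of the four-woman 80 mg cohort "whether we observe PDI inhibitory activity in plasma using Di-eosin-GSSG assay". The background (section 2.1) gives the reason: at 40 mg "there was only modest inhibition of PDI activity in plasma". The caption to Figure 4 describes that result as "Inhibition of plasma PDI activity before and 28 days following initiation of zafirlukast".

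**CA-125 doubling.** Section 1.5 takes a woman off therapy once a doubling is confirmed by a second value a week or more later, with no upper limit. Section 7.2 defines CA-125 progression by confirmation 1 to 3 weeks after the first value and keeps her on drug until progression is confirmed. Section 7.1 and the calendar schedule on-treatment CA-125 every 4 weeks.

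**The concern.** The supply has two days of slack and the visit has seven. A visit that breaks no rule can therefore find a woman who took every dose with no tablets left. The sample drawn that day would be analysed as on-treatment. If inhibition fades as drug clears, it would be read as weaker inhibition at 80 mg. The 40 mg result it will be set against is reported at 28 days, inside the supply, so the dose comparison would be blurred too.

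The CA-125 mismatch is a separate matter. The nominal interval between scheduled draws satisfies the stopping rule but not the progression rule. The same pair of values can end treatment without counting as progression, so the off-treatment reason and exploratory PFS can disagree for one woman.

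**Working it through.** The plan gives no figure of its own to reproduce here, so the check is day counts and decay arithmetic.

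**A. Inputs.** Cycle 28 days (section 1.1); supply 30 days at two doses a day, or 60 doses (sections 1.3 and 4.1.6); window ±7 days (section 6); four 20 mg tablets per dose at 80 mg, or 8 a day (section 1.3). For half-life, section 4.1 gives about 10 h in the pivotal study and, for other studies, says "the mean plasma half-life of zafirlukast ranged from approximately 8 to 16 hours". Assumptions: full adherence, 12 h dosing, and a morning draw before that day's dose.

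1. Latest compliant C2D1 = Day 29 + 7 = Day 36.
2. With two doses on Day 1, dose 60 falls on the evening of Day 30. With the first dose on the evening of Day 1, dose 60 falls on the morning of Day 31.
3. Drug level relative to the usual 12 h trough = 2^(−(h − 12)/half-life), where h is hours since the last dose.

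| Morning draw | Start of dosing | h | 8 h half-life | 10 h half-life | 16 h half-life |
|---|---|---|---|---|---|
| Day 31 | either | 12 | 100% | 100% | 100% |
| Day 32 | evening of Day 1 | 24 | 35% | 44% | 59% |
| Day 32 | two doses on Day 1 | 36 | 12.5% | 19% | 35% |
| Day 36 | evening of Day 1 | 120 | under 1% | under 1% | 0.93% |
| Day 36 | two doses on Day 1 | 132 | under 1% | under 1% | 0.55% |

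4. A draw up to Day 31 (+2 days) is a normal trough. Days 32 to 36 (+3 to +7 days) are the exposed days. Skipped doses leave tablets over and push the run-out later; lost tablets bring it forward.
5. Tablets at 80 mg twice daily: current supply 8 × 30 = 240. To reach a pre-dose draw on Day 36, 8 × 35 = 280. Keeping the present two-day reserve, 8 × 37 = 296. Increase: 296 − 240 = 56 per woman, or 56 × 4 = 224 for the cohort.

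**B. CA-125 confirmation.** Let g be the gap in days between the first doubled value and its confirmation. Section 1.5 needs g ≥ 7; section 7.2 needs 7 ≤ g ≤ 21.

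| g (days) | Stops drug (1.5) | CA-125 progression (7.2) |
|---|---|---|
| 7, 14, 21 | yes | yes |
| 22, 28, 35 | yes | no |

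The nominal scheduled gap of 28 days is 28 − 21 = 7 days past the section 7.2 limit. The calendar shows no conditional repeat draw after a first doubling.

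**The case against.** **On A.** This is a conditional operational risk: it needs a visit at least 3 days late together with near-full adherence, and the documents do not say how often visits run late. The only timing evidence, from the 40 mg cohort, is 28 days. Both limits stand, and they are why the claim is that a sample may be off drug, not that it will be.

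The dose diary, its review at C2D1 and the pharmacy count of returned tablets could reveal an off-drug sample. They could not restore it. The Off Treatment correlative sample may still contain drug, but it is not in the planned test. The window sentence also covers medications, so it could be read as permitting early dispensing; no procedure for that is described.

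A larger pack might seem to weaken liver monitoring, since section 3.1.1 associates most liver-enzyme elevations in trials with four times the recommended dose, which is 80 mg twice daily. Chemistry is due on Day 22, so a Day 36 visit means 14 days between tests. That is shorter than the 28-day interval the calendar already accepts from Cycle 3, so the objection is weak.

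A reader might infer that one off-drug sample puts statistical significance out of reach with four women. The documents do not support this. It would need a difference of exactly zero, the 80 mg cohort tested alone (section 9.5 does not say so) and a 0.05 level that the protocol never states. For PDI, section 9.2 asks only whether inhibition is observed.

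**On B.** One to three weeks lies inside a week or more, so a repeat drawn as section 7.2 directs meets both rules. That stands: the rules do not contradict each other outright. They part only when confirmation waits for the next scheduled draw.

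**Conclusion.** Both parts hold, within limits.

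**A.** The stated cycle, supply and window allow a compliant C2D1 on Days 32 to 36, about 1 to 5 days after a fully adherent woman has run out. Drug would be about 12-59% of trough on Day 32 and under 1% on Day 36. Each such sample is a quarter of the 80 mg cohort's data for the planned PDI test. The expected direction is understated inhibition, on the assumption that inhibition falls with plasma drug; the documents do not link drug level to the assay. Nothing here casts doubt on the 40 mg PDI result.

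**B.** A doubling confirmed at the nominal 28-day draw ends treatment without being a CA-125 progression under section 7.2. The effect is confined to the off-treatment reason and exploratory PFS. Symptoms or radiographic disease could still establish progression.

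A reader might also infer that the ±7-day window undermines the primary endpoint, because response must be held for 28 days and draws are nominally 28 days apart. The documents do not support a material effect: with up to 12 cycles of draws, a short gap usually only delays confirmation to the next one. The CA-125 response rate and the doubling-time comparison are not at issue here.

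**What to change.** **A.** For Cycle 1 of the 80 mg cohort, do one of two things:

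- Dispense 37 days of tablets: 296 instead of 240, with 280 as the bare minimum. Cost: 56 extra tablets per woman, 224 for four women.
- Keep the present pack and allow the C2D1 correlative draw no later than +2 days (Day 31). Cost: a tighter late limit for one visit, with no spare tablets if it falls on Day 31.

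With either, record the date and time of the last dose at that draw. The diary already covers each dose, but the documents do not say that it records the time. Cycle 1 is enough, because later cycles supply no sample to this test.

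**B.** Require confirmation at least 1 week after the first doubled value in both sections 1.5 and 7.2. This is one wording change and needs no extra draw, because the 4-weekly schedule can meet it. Putting 1 to 3 weeks in both sections is less good: a doubling first confirmed at week 4 would then no longer trigger the CA-125 stopping rule. Section 7.2 cites published criteria that were not available for this review, so the report should state the confirmation interval used.

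Neither change alters the sample size or the choice of endpoints.
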